10.4.2 Secondary efficacy endpoints

Overall survival

Overall Survival (OS) is defined as the time from the date of start of treatment to the date of death due to any cause. The survival time for patients without documentation of death prior to the data cutoff, will be censored at the last date the patient was known to be alive prior to the cutoff date. Survival time for patients with no post-baseline survival information will be censored at the date of start of treatment. OS will be analyzed using the Kaplan Meier method. Survival rate at 4, 6, 8, 12, 18 and 24 months and median OS will be estimated along with 95% confidence intervals from the Kaplan Meier distribution. The FAS will be used.

Progression Free Survival

Progression free survival (PFS) is defined as the date of the start of treatment to the date of the event defined as the first documented progression or death due to any cause. If patient has not had an event, progression-free-survival is censored at the date of last adequate tumor assessment. Kaplan-Meier analysis of PFS will be conducted for each cohort.

Best Overall Response and Disease Control Rate.

Overall lesion assessments will be listed by patient. Best overall response (BOR) will be summarized for the each cohorts using the Overall Response Rate and the Disease Control Rate which are the proportion of patients having respectively a best overall response of PR or CR, or SD, PR or CR. The estimated ORR and corresponding 90% confidence intervals based on the binomial distribution will be reported.

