4.4 Definition of end of the study

End of study is defined as the time when the last patient completes the survival follow-up as described in Section 7.1.6 or when the last patient on study has expired, been lost to follow-up, or withdraws consent, whichever occurs first or when the study is terminated early.

The analysis of study data will be based on all patients' data up to the time when all patients have completed at least 6 cycles of treatment or discontinued the study. This will be the cutoff point for the primary clinical study report (CSR). The additional data for any patients continuing to receive Infigratinib, or remain in safety or survival follow-up beyond the cut-off point will be summarized in a final CSR that will be prepared once all patients have either discontinued or completed the study i.e. end of survival follow-up period which is defined as the time when all patients have discontinued study and at least 80% of the patients have died, withdrawn consent, or been lost to follow-up.

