7.1.6 Follow-up period

Patients lost to follow-up should be recorded as such on the eCRF. For patients who are lost to follow-up, the Investigator should show "due diligence" by documenting in the source documents steps taken to contact the patient, e.g. dates of telephone calls, registered letters, etc.

30-day safety follow-up period

All patients must complete the safety follow-up assessments 30 days after the last dose of the study treatment. Information relating to antineoplastic therapies taken since discontinuation of study treatment and AEs (including concomitant medication taken for ongoing AEs) will be collected for 30 days after the last dose of the study treatment.

All AEs suspected to be related to study drug should be followed up weekly, or as clinically indicated, until resolution or stability.

Disease progression follow-up period

All patients enrolled in the study who discontinue study treatment for any reason other than disease progression will have a tumor assessment every 8 weeks (\pm 7 days), until disease progression or the initiation of subsequent anticancer therapies, or death, whichever occurs first. Any newly started antineoplastic therapies during the follow-up period must be recorded on the Antineoplastic therapy since discontinuation eCRF.

Survival follow-up period

All patients enrolled in the study will be followed for survival every 4 months for one year after discontinuation of treatment. Survival follow-up will continue until all patients have discontinued study and at least 80% of the patients have died, withdrawn consent, or been lost to follow-up.

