- Date of last contact is defined as the last date the patient was known to be alive. This corresponds to the latest date for either the visit date, lab sample date or tumor assessment date. If available, the last known date patient alive from the survival follow-up page is used. If no survival follow-up is available, the date of discontinuation is used as last contact date.
- Date of secondary anti-cancer therapy is defined as the start date of any additional (secondary) antineoplastic therapy or surgery.

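### Overall survival can be understated because survivors are censored at their last contact before cut-off, while a death learnt between contacts counts at its true date

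*Combined protocol and SAP*

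**What the plan says.** Section 10.4.2 defines OS from start of treatment to death from any cause, estimated by Kaplan-Meier, with rates at 4, 6, 8, 12, 18 and 24 months and a median. On censoring it says that survival time, for anyone whose death is not documented by then, "will be censored at the last date the patient was known to be alive prior to the cutoff date".

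Section 13.3.24 builds the last-alive date from contacts: the latest visit, laboratory or tumour-assessment date. It adds: "If available, the last known date patient alive from the survival follow-up page is used".

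Section 7.1.6 sets how often those contacts happen:

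- Patients off drug without progression have 8-weekly tumour assessments until progression, new anticancer therapy or death.
- For survival, "All patients enrolled in the study will be followed for survival every 4 months for one year after discontinuation of treatment".
- The next sentence gives a different end point: "Survival follow-up will continue until all patients have discontinued study and at least 80% of the patients have died, withdrawn consent, or been lost". Section 4.4 repeats the 80% rule.

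The primary report uses data "up to the time when all patients have completed at least 6 cycles of treatment or discontinued the study" (Section 4.4). Neither 4.4 nor 10.4.2 asks for survival status to be established at that date.

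**The concern.** Kaplan-Meier needs censoring that carries no information about the outcome. Take two patients last contacted on the same day, some weeks before cut-off. One dies before cut-off and a relative reports it; that patient contributes follow-up and an event at the date of death. The other is alive at cut-off but contributes nothing after the last contact. Within that interval the events are counted and much of the survivors' time at risk is not, so the hazard is too high and survival too low.

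At stake are the published landmark rates and median. The later rates are the most exposed, since few patients remain at risk there.

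**Working it through.** The documents give no assumed OS median, event count or power, so there is no figure of the plan's own to reproduce. The check is a simulation.

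**Inputs from the documents**

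- Contacts: every 28 days on drug, at end of treatment, at 30 days, then every 4 months (Table 7, Section 7.1.6).
- Primary cut-off: six 28-day cycles after the last first dose. 6 × 28 = 168 days, and 168 / 30.4 = 5.5 months.
- Time on drug: median 5.8 months. This is a proxy, the PFS of the earlier cholangiocarcinoma study (Section 1.2.1.4.2).

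**Assumptions not in the documents**

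- Exponential OS with median 12 months, so S(t) = 0.5^(t/12), giving S(12) = 50% and S(24) = 25%.
- Uniform accrual over 24 months.
- A share q of the deaths falling between the last scheduled contact and the cut-off is learnt off-schedule and counted: 0, 0.5 or 1.
- The 8-weekly scans for patients off drug without progression are left out, which slightly enlarges the gap.

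**Rule as written, 400,000 simulated patients per row**

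| Survival contact | q | 12-month OS | 24-month OS | Median (months) |
|---|---|---|---|---|
| Continues every 4 months | 0 | 49.9% | 24.8% | 12.0 |
| Continues every 4 months | 0.5 | 49.2% | 23.1% | 11.7 |
| Continues every 4 months | 1 | 48.7% | 21.2% | 11.6 |
| Stops 1 year after treatment | 0 | 50.0% | 24.8% | 12.0 |
| Stops 1 year after treatment | 0.5 | 49.2% | 16.9% | 11.7 |
| Stops 1 year after treatment | 1 | 48.8% | 13.2% | 11.6 |

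With everyone's status known at cut-off, the same code returns about 50%, 25% and 12.0 months. So with contacts continuing and q = 1 the losses are 50 − 48.7 = 1.3 points, 25 − 21.2 = 3.8 points and 12.0 − 11.6 = 0.4 month.

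**Size of the gap.** With contacts continuing, a survivor is censored at most 4.0 months before cut-off, on average about 1.3 to 1.6 months. If contact stops at one year, the earliest-enrolled patient has 24 + 5.5 = 29.5 months to cut-off. If that patient came off drug almost at once, the gap is 29.5 − 12 = 17.5 months.

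**Range.** With true medians of 8 to 18 months, accrual over 24 to 36 months, contacts continuing and q = 1, the loss is 0.7 to 1.4 points at 12 months, about 1 to 4 points at 24 months and 0.1 to 1.1 months in the median. With 12-month accrual the 12-month loss is about 3 to 4 points. In no setting did the rule materially raise survival.

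**Yardstick.** In 4,000 simulated trials of n = 30 (Cohort 1), the sampling SD of the OS estimate was about 10 points at 12 months and 12 points at 24 months.

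**The case against.** The strongest reply is that the asymmetry comes from reading the sentence unevenly. If information stops at cut-off for everyone, a death first learnt later is not documented in time and is not an event. If later information counts for everyone, a patient reached alive after cut-off was known to be alive up to it, and the existing words already censor there, or nearly so. This is fair, and each reading shrinks the problem. But the text does not choose between them, and under the first an unscheduled death report received before cut-off is still treated differently from an unreported survival.

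A reader might infer that survival *is* understated. The documents do not support that. If deaths are learnt only at the same scheduled contacts as survival, both are ascertained alike and the bias nearly vanishes (the q = 0 rows). Nor do they support assuming q = 0 throughout. A death within 30 days of last dose is a serious adverse event that sites must notify within 24 hours of learning of it (Sections 8.2.1 and 8.2.2.2). Later serious events are reportable if a causal link is suspected (8.2.2), and family or physician may be contacted when a patient misses visits (7.1.7). Beyond 30 days the share learnt off-schedule is simply unknown.

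A reader might also infer a 4-month gap for everyone off drug. It applies mainly after progression or new therapy, because the others have 8-weekly scans. It is also too short a bound if contact ends at one year.

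Finally, OS is a secondary endpoint with no test, in a study that Section 4.2 calls signal-finding, and a final report follows the primary one. All of that stands, and it limits the weight of the point.

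**Conclusion.** The concern holds in conditional form. OS can be understated; whether it is, and by how much, depends on the share of deaths learnt between scheduled contacts, which the plan leaves open.

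Under the base assumptions with contacts continuing, the loss is at most about 1.3 points at 12 months and 4 points at 24 months. Both are small beside the sampling SDs of about 10 and 12 points at n = 30. The exception is the 24-month rate if contact really ends at one year: with all deaths learnt, the fall of about 12 points (25% to 13%) is as large as one SD. The conflict between the one-year and 80% rules therefore matters more than the 4-month interval.

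These sizes rest on exponential survival, an assumed accrual period, and a time on drug borrowed from a cholangiocarcinoma study, a tumour type excluded from Cohort 1. No decision rule depends on OS. This is a cheap improvement worth making, not a flaw in the trial's main conclusion.

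**What to change.** 1. In Section 10.4.2, state that only deaths on or before the data cut-off are events; that patients known to be alive on or after the cut-off, from any contact or record before database lock, are censored at the cut-off date; and that last-contact censoring applies only to patients with no status at or after the cut-off. Align Section 13.3.24 with this.
2. Obtain vital status by phone or records for each patient still in survival follow-up, shortly after each cut-off (within about 4 weeks, say).
3. Reconcile the one-year and 80% survival follow-up rules in Sections 4.4 and 7.1.6, so that the 18- and 24-month rates rest on a defined contact schedule.

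The cost is a short text change and one call or record check per living off-treatment patient at each cut-off. Treatment, eligibility and sample size are untouched. Status that was never collected cannot be fully recovered later, so the check should be in place before the primary cut-off.

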10.5 Safety analysis

Exposure to study drug and study drug compliance will be tabulated.

Safety analyses will be performed on the Safety population, and safety endpoints will be tabulated and presented. All AEs occurring during the study will be included in by-patient data listings and tabulated by organ class and preferred term. Adverse events will be summarized overall, by relationship and by severity. Events leading to death, SAE, and events resulting in treatment discontinuation will be tabulated.

The actual value and change from Baseline to each on-study evaluation will be summarized for vital sign measurements, as warranted by the data. By-patient listings of vital sign measurements will be prepared. Individual patient laboratory parameter values and summary statistics over time will be prepared using descriptive statistics. Severity of select clinical laboratory measures will be determined using NCI CTCAE v5 criteria and Grade 3 or 4 laboratory values will be presented in a separate patient listing.

The use of concomitant medications, coded using World Health Organization Drug Dictionary, will be included in by-patient listing.

Additional safety analyses may be performed to most clearly enumerate rates of toxicities and to further define the safety profile of this drug.

11. Ethical considerations and administrative procedures

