1.2.1.4 Clinical experience

1.2.1.4.1 Clinical safety

As of the cutoff for the Investigator's Brochure v10, 453 patients and 134 healthy volunteers have received infigratinib, alone or in combination, in 4 healthy volunteer, two phase 1, one phase 1b, and three phase 2 trials. All trials have completed with the exception of the ongoing phase 2 CBGJ398X2204 study of infigratinib in patients with advanced or metastatic cholangiocarcinoma with FGFR2 gene fusions/translocations or other FGFR genetic alterations.

The treatment emergent adverse events, regardless of relationship to infigratinib, reported for the CBGJ398X2204 study as of 01 June 2017, that occurred in $\geq 20\%$ of subjects were: hyperphosphatemia (82.5%), fatigue (49.2%), constipation (41.3%), stomatitis (38.1%), alopecia (38.1%), dysgeusia (31.7%), blood creatinine increased (27.0%), hypophosphatemia (27.0%), nausea (27.0%), diarrhea (25.4%), dry eye (25.4%), arthralgia (23.8%), dry mouth (23.8%), dry skin (23.8%), palmar plantar erythrodysesthesia syndrome (23.8%), aspartate aminotransferase increased (22.0%), decreased appetite (20.6%), and hypercalcemia (20.6%).

Grade 3 or 4 events that occurred in $\geq 5\%$ of subjects were hyperphosphatemia (15.9%), hypophosphatemia (6.3%), hyponatremia (12.7%), lipase increased (7.9%), and stomatitis (7.9%).

Hyperphosphatemia is a pharmacodynamic marker of on-target FGFR pathway inhibition seen in the majority of subjects treated at doses of ≥ 100 mg/day. Renal tubular phosphate secretion and reabsorption are controlled through the FGFR1 pathway. Inhibition of this pathway leads to inability to secrete phosphate and secondary elevations in fibroblast growth factor 23. The hyperphosphatemia has been managed by dietary phosphate restrictions, phosphate lowering therapy, and drug interruptions and dose reductions, which led to the introduction of the alternate 3 weeks on/1 week off drug schedule.

Ocular AEs were frequent, but were generally mild to moderate in severity and reversible. Corneal or retinal AEs were recognized on ophthalmologic evaluations.

No effect of infigratinib on electrocardiogram (ECG) intervals, including QTc, has been noted. Reversible and largely asymptomatic decreases in left ventricular ejection fraction (LVEF) have been noted in subjects enrolled on study, as measured by serial transthoracic echocardiography or multiple gated acquisition (MUGA) scans.

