Tumor response per RECIST 1.1	D	X							X		Day 1 of every odd cycle	X (if not done within 28 days prior)		X (only for pts. who discontinue)	

	Category	Screening	Cycle 1			Cycle 2		Cycle 3		Subsequent cycles	End of study treatment	30-day follow-up (end of study)	Disease Progression follow-up every 8 weeks	Survival follow-up (every 4 months after EOT for 1 year)
Study Period			Treatment									EOT	Follow-up	
Day of Cycle		-28 to -1	1	8	15	21	1	15	1	15	1	≤14 days of decision to discontinue treatment		
													for any reason other than progression of disease	
Study drug administration			Continuous on a 3 weeks on 1 week off schedule											
12-lead ECG	D	X	X		X		X		X		X	X		
Cardiac imaging (ECHO or MUGA)	D	X				X						X		
Adverse Events	D	Continuously throughout the study												
Collection of archival paraffin blocks/slides or a newly obtained tumor sample AND pathology report	D	X												
Newly obtained tumor sample (if medically feasible)	D	X ^a	X (mandatory on-treatment biopsies occurring at the end of Cycle 2 and upon disease progression)											
Blood sample for assessment of circulating tumor DNA (ctDNA)	D	X	X		X		X	X	X	X	Day 1 of every cycle	X (if not done within 28 days prior)		
Survival follow-up	D													X
Antineoplastic therapies since discontinuation of study treatment	D											X	X	
Disease progression follow-up													X	

^a Sample will not be collected if a fresh tumor sample has already been collected at baseline for the purpose of DNA sequencing.

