7.2.2.1 Physical examination

A complete physical examination must be performed as indicated in **Table 7**.

Physical examination will be performed on the scheduled day, even if study treatment is being withheld. More frequent examinations may be performed at the discretion of the Investigator and if medically indicated.

A complete physical examination will include the examination of general appearance, skin, neck (including thyroid), eyes, ears, nose, throat, lungs, heart, abdomen, back, lymph nodes, extremities, vascular and neurological. If indicated based on medical history and/or symptoms, rectal, external genitalia, breast, and pelvic exams will be performed.

Information about the physical examination must be present in source documentation at the study site. Significant findings that are present prior to signing of informed consent form for the study must be included in the Relevant Medical History/Current Medical Conditions page on the patient's eCRF. Significant new findings that begin or worsen after informed consent for the study must be recorded on the AE eCRF.

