8.1.4 Reporting adverse events

For all enrolled patients, AEs should be recorded on the eCRF beginning with signing of the informed consent form and concluding 30 days following the last dose of the assigned study treatment, or the investigator/patient decision to discontinue treatment, whichever occurs later.

AEs ongoing after the reporting period: Any ongoing AEs thought to be at least possibly study-drug related after this time should be followed and reported to the sponsor's medical monitor until they resolve to baseline (or CTCAE grade ≤ 1), stabilize, or are considered to be chronic/irreversible.

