8.2.2 Reporting serious adverse events

Serious AEs require immediate notification by the investigator or designee to QED Therapeutics Corporation beginning from the time the patient provides informed consent (ie, prior to undergoing any study-related procedure and/or receiving investigational product), through and including 30 days after the last administration of study treatment, or the investigator/patient decision to discontinue treatment, whichever occurs later. Any SAE occurring any time after the reporting period must be promptly reported to QED Therapeutics immediately after becoming aware of the SAE if a causal relationship to the investigational product is suspected. All SAEs ongoing 30 days or more after last dose of study drug is administered should be followed at least every 4 weeks until they resolve to baseline (or CTCAE grade ≤ 1), stabilize, or are considered to be chronic/irreversible. Should the FDA or national regulatory authorities require that the sponsor submit additional event data, the investigator will be asked to provide those data to the sponsor in a timely fashion.

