8.2.2.1 Serious adverse event reporting period

The Ohio State University will be solely responsible for reporting serious adverse events to the OSU IRB, FDA, and QED Therapeutics. Participating subsites report directly to OSU and must report serious adverse events to the OSU PI and Multi-Site Coordinator within 24 hours of knowledge of the event. Serious adverse events are to be reported to the OSU IRB (per policy), FDA (per 21CFR312.32), and the appropriate monitor or subcommittee or task force within QED Therapeutics or its designated representative beginning from the time the patient is first administered investigational product through and including 30 days after permanent discontinuation of the investigational product. Any SAEs occurring any time after the reporting period must be promptly reported to the OSU IRB (per policy), FDA (per 21CFR312.32) and QED Therapeutics if a causal relationship to the investigational product is suspected.

Patients must be followed for all AEs from the date the patient is first administered investigational product until at least 30 Days after the End of Treatment, and for all serious or study drug-related toxicities until the AEs are resolved or until patient contact discontinues.

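### Section 10.5 sets no event window for the adverse-event tables, so with recording from consent, pre-dose events enter the all-cause, severity and SAE rates

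*Combined protocol and SAP*

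**What the plan says.** Section 10.5 gives the tabulation rule: "All AEs occurring during the study will be included in by-patient data listings and tabulated by organ class and preferred term". It then asks for summaries overall, by relationship and by severity, and for tables of SAEs, events leading to death and events leading to treatment discontinuation. It gives no onset window and no comparison with baseline grade. These analyses use the Safety Set, which section 10.2 defines by patient: at least one dose and at least one valid safety assessment after baseline.

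Several places start data collection at consent:
- Section 8.1.4: "AEs should be recorded on the eCRF beginning with signing of the informed consent form and concluding 30 days following the last dose" (or the decision to discontinue, if later).
- Table 7, adverse-event row, marked as entered in the database: "Continuously throughout the study".
- Section 7.2.2.1: "Significant new findings that begin or worsen after informed consent for the study must be recorded on the AE eCRF".
- Section 8.2.2, for SAE notification: "beginning from the time the patient provides informed consent".

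Two places point to the first dose instead:
- Section 8.2.2.1: "Patients must be followed for all AEs from the date the patient is first administered investigational product until at least 30 Days", counted from the end of treatment. It gives the same start for SAE reporting.
- Section 8.1.1 ties worsening of a pre-existing condition to the time after the first dose, but sets no such limit on new events.

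The plan does not define a treatment-emergent event for this trial. The term appears in section 1.2.1.4.1, for an earlier study: "The treatment emergent adverse events, regardless of relationship to infigratinib, reported for the CBGJ398X2204 study".

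**The concern.** The type, frequency and severity of adverse events make up secondary objective 2 (Table 3). The trial has a single arm, so no control group offsets background events. Patients have advanced, previously treated cancer, and screening may last up to 21 days (28 for imaging). New symptoms or procedure-related events between consent and the first dose are therefore plausible.

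If the tables count them, the all-cause incidence describes a period that starts before exposure. The error runs in one direction: an added pre-dose event can raise the proportion of patients with a term, or with a term at or above a given grade, but cannot lower it. The rates are also on a different basis from the treatment-emergent rates in section 1.2.1.4.1, so a reader who sets the two side by side would not be comparing like with like.

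**Working it through.** The plan states no adverse-event rate, so there is no figure to reproduce. The check is a reading of the rules, followed by arithmetic on the weight of one patient and an illustration under assumed rates.

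**Step 1: does any rule remove a pre-dose event from the tables?** Take a patient who signs consent, has a new event in screening, is then dosed, and has a later safety assessment.
- 8.1.4, Table 7 and 7.2.2.1: the event is on the eCRF and in the database.
- 10.2: the patient is in the Safety Set. The event date is not tested.
- 10.5: the event falls during the study, so it is tabulated.
- 8.1.6: an onset that cannot reasonably follow from dosing is classed as definitely not related. The event leaves the drug-related count but stays in the overall, preferred-term and severity counts, and in the SAE count if serious.
- 8.2.2.1: on this text, follow-up for events starts at first dose and the event might not be captured. Section 10.5 does not adopt this as its window.

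Events in screen failures are not counted, because those patients are never dosed.

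**Step 2: weight of one patient.** Section 10 analyses each cohort separately unless otherwise stated. Assume that the full planned numbers enter the Safety Set.
- Cohort 1: 1/30 = 3.3 percentage points.
- Cohorts 2 and 3: 1/10 = 10 percentage points.

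**Step 3: illustration.** Let p be the proportion of patients with a given term after first dose and q the proportion with it before first dose. Neither is in the documents. Assuming independence, the tabulated proportion is 1 − (1 − p)(1 − q).

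| p (post-dose) | q = 2% | q = 5% | q = 10% |
|---|---|---|---|
| 5% | 6.9% | 9.8% | 14.5% |
| 10% | 11.8% | 14.5% | 19.0% |
| 50% | 51.0% | 52.5% | 55.0% |

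For example, p = 5% and q = 5% give 1 − 0.95 × 0.95 = 0.0975.

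The chance of at least one pre-dose event in a cohort of N is 1 − (1 − q)^N. For q = 2%, 5% and 10% it is 18%, 40% and 65% at N = 10, and 46%, 79% and 96% at N = 30.

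The distortion is largest for uncommon terms and small for common ones. The assumed q values show a range and are not estimates.

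**The case against.** The strongest reply is that the protocol does not speak with one voice on when adverse events start. Section 8.2.2.1 starts at first dose, and 8.1.1 limits worsening of existing conditions to the time after first dose. On that reading fewer pre-dose events would reach the database. This stands as a limit on the size of the effect. It does not remove the problem: 10.5 adopts neither window, so two programmers could build different tables from the same plan.

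Three stronger readings are tempting, and the documents do not support them.
- A reader might infer that pre-dose events would be reported as toxicity caused by infigratinib. The by-relationship summary and the causality scale in 8.1.6 argue against this. The exposed tables are the all-cause ones. The table of events leading to treatment discontinuation can hardly be affected.
- A reader might infer that the rates in 1.2.1.4.1 are the yardstick for the risk/benefit review in 8.3.2. That section refers to outside sources in general terms, does not name those rates, and does not say that the review uses the 10.5 tables. Only the difference in basis can be claimed.
- A reader might infer that every patient brings a screening biopsy, and so a source of complications, into the tables. Section 7.2.3.1 accepts archival tissue, although 7.2.3.4.1 calls a pre-treatment biopsy mandatory. A treatment-emergent rule would also leave in the complications of on-treatment biopsies; causality attribution has to deal with those.

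It is also fair to say that the eligibility criteria limit pre-dose overlap with some known effects of the drug, since phosphorus and calcium must be normal and corneal or retinal disorders are excluded. Section 10.5 also permits additional safety analyses. That permission is optional and does not alter the stated rule for the main tables.

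**Conclusion.** The point holds as a gap in the safety-reporting definition. Combined with recording from consent, 10.5 counts pre-dose events of later-dosed patients in the all-cause, preferred-term, severity and SAE tables, and the effect on those incidences can only be upward. Drug-related tables are largely protected.

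The size is unknown, because the documents give no pre-dose event rate. What can be stated is the weight of each patient whose only occurrence of a term is pre-dose, as worked out above.

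This rests on three assumptions: section 8.1.4 governs what is recorded, incidence is counted per patient, and the planned cohort sizes are reached. If 8.2.2.1 governed instead, fewer pre-dose events would be captured, but the plan would still lack a stated window. The matter concerns a descriptive secondary objective and does not touch the response-rate analysis or the two-stage rule in Cohort 1. It should be corrected before the tables are programmed.

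**What to change.** In section 10.5, define a treatment-emergent adverse event as one with onset, or worsening in grade from baseline, on or after the first dose and up to the end of the reporting period in 8.1.4, plus later events judged related to study drug. Base the overall, preferred-term, SAE, severity and relationship summaries on these events. List events before the first dose separately, so that nothing collected is lost.

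Reconcile the start of adverse-event and SAE recording across 8.1.1, 8.1.4, 8.2.2 and 8.2.2.1, so that the database contents and the analysis window are each stated once.

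The cost is one added definition and a flag derived from event dates and grades and the date of first dose. No new assessment is needed.
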